3.6 Laboratory methods

Primary care practitioners will collect respiratory specimens from either all or a systematic sample (see section 3.7.1) of eligible patients (meeting the case definitions above and consenting to take part in the study), respecting safety standards for influenza and COVID-19 and following WHO biosafety guidelines³. Depending on the setting, some practitioners will refer patients to specific testing centres or medical laboratories.

It would be beneficial if those countries only measuring CVE test for both SARS-CoV-2 and influenza during the influenza season, as well as for all other respiratory viruses (as appropriate depending on time of year), if possible. If this is not feasible, then during influenza season all samples that are negative for SARS-CoV-2 should also be tested for influenza.

- *Each study site to describe the type (nasopharyngeal/oropharyngeal or both) and number of swabs taken for each patient.*
- *Each study site to describe where swabbing will be carried out (at practice, at home, in centres, a mixture).*
- *Each study site measuring only CVE to indicate which testing strategy they will use (testing all samples for both SARS-CoV-2 and influenza, or only testing for influenza in those negative for SARS-CoV-2).*
- *Each study site to indicate whether they can test for other respiratory viruses, or only SARS-CoV-2 and influenza, or only SARS-CoV-2.*

Quality control tests should systematically be run using PCR to ensure presence of human cells in the respiratory specimens. In the absence of cells, a negative result should be considered inconclusive and a second swabbing should take place if possible.

The ECDC-recommended influenza and SARS-CoV-2 laboratory confirmation is by viral RNA detection with nucleic acid amplification tests, such as RT-PCR. Isolates will undergo molecular analysis for currently circulating SARS-CoV-2 virus.

Information will be collected on type of test.

Following the procedures outlined by each study, a systematic sample of isolates (or all isolates) will undergo gene sequencing. The sampling procedure can include sequencing all isolates, or a random sample thereof. The sample should be random and thus be representative of cases and be large enough to provide reasonable precision when calculating proportions of virus change over time.

Gene sequences should also be uploaded to GISAID's open access EpiFlu (influenza) or EpiCoV (SARS-CoV-2) platform. The GISAID EpiFlu/EpiCoV accession number can be provided alongside the epidemiological data, or stored separately along with a unique identifier for the epidemiological data. If random selection of viruses to sequence is used, the proportion sequenced may vary over time, according to a variety of factors, including resources and incidence of influenza virus or SARS-CoV-2. Study sites should indicate their sampling fraction for sequencing over time (see Annex 2, Table 9). Processed genetic information, e.g. name of genetic clade, can also be included within the epidemiological database.

- *Each study site to describe the laboratory procedures (samples taken, storage, transport).*

³ Any non-propagative diagnostics (e.g. sequencing, RT-PCR) should be conducted at a facility using procedures equivalent to biosafety level 2 (BSL-2), while propagative work (e.g. virus culture, isolation, or neutralisation assays) should be conducted at a containment laboratory with inward directional airflow (BSL-3). Patient specimens from suspected or confirmed cases should be transported as UN3373, 'biological substance category B'. Viral cultures or isolates should be transported as category A, UN2814, 'infectious substance, affecting humans'. World Health Organization (WHO). End-to-end integration of SARS-CoV-2 and influenza sentinel surveillance: revised interim guidance, 31 January 2022. Available at: <https://apps.who.int/iris/handle/10665/351409?locale-attribute=pt&>

- *Each study site to describe the tests and the kits used (and their sensitivity, specificity, positive predictive value) for influenza virus and SARS-CoV-2 and, if needed, other respiratory virus detection.*
- *Each study site to describe if the laboratory participates in QA/QC (Quality Assurance/Quality Control) schemes.*
- *Each study site to describe the selection of specimens and the methods for genetic and, when it becomes available, antigenic characterisation.*
- *Each study site to describe genetic and, when it becomes available, antigenic analyses and specify sequencing methods, as well as describing numbers of viruses not sequenced due to CT values or other technical reasons (see Annex 2, Table 9).*

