2.2 Secondary objectives

The secondary objectives are to measure overall and product-specific IVE and CVE against symptomatic laboratory-confirmed influenza or SARS-CoV-2 infection, by:

- risk groups (such as clinically vulnerable people, pregnant women, etc.);
- sex;
- age groups;
- specific vaccination target groups;
- calendar time;
- time since vaccination;
- vaccine schedules;
- delay between doses (if more than one dose received);
- combination of vaccine products (if applicable).

Secondary objectives include also identifying key phenotypic or genotypic evolutions that could affect vaccine performance and to estimate IVE and CVE against specific influenza (sub)clades or SARS-CoV-2 genetic variants.

- *Each study site/country to specify primary objectives of their study as measuring CVE and IVE or CVE only or IVE only.*
- *Each study site/country to specify the (additional) secondary objectives of their study.*

¹ Countries only participating in CVE can ignore references to measurement of IVE throughout the document and vice versa.

3 Methods

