3.4 Outcomes

IVE studies

The primary outcome of interest will be PCR laboratory-confirmed influenza in symptomatic patients of all ages consulting at primary care level. The specific outcomes of interest are:

- subtype-specific laboratory-confirmed influenza A;
- laboratory-confirmed influenza B overall and, if available, by lineage (B Victoria/B Yamagata); and
- laboratory-confirmed influenza by clade/genetic variant (where possible).

CVE studies

The primary outcome of interest will be PCR laboratory-confirmed SARS-CoV-2 in symptomatic patients of all ages consulting at primary care level. Confirmation with rapid-diagnostic tests can be considered if highly specific and sensitive tests are used (see section 3.6 on 'laboratory methods').

Secondary outcomes of interest, in the same patient group at primary care level, will be genetic variants of SARS-CoV-2.

² The end of the study period could be defined as the week before two consecutive weeks of no influenza cases after the peak.

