Annex 2. Genetic information (examples)

Information related to genetic sequencing can be included in the epidemiological database, or provided separately in a spreadsheet, as below. The minimum amount of data needed to obtain genetic data from GISAID (sequences of all viruses should be sent to GISAID's open access EpiCoV platform) is ID number and GISAID accession number. Additional information on CT value, selection for characterisation, and reasons for not characterising can be additionally collected (see Table A2).

Table A2. Example of a data collection form for genetic data

[figure not shown]
	Unique ID number	GISAID accession ID number	Selected for characterisation?	Reasons for not characterising?	CT value	Type of sample (primary specimen or isolate)
Strain 1						
Strain 2						

Where not all viruses were attempted to be sequenced, but only a random selection of them, additional information on sampling fraction should be provided. An example can be seen in Table A3.

Table A3. Example of documenting how viruses were selected for sequencing over time

Time period	First date of time period	Last date of time period	Sampling fraction used	Date used for definition of time unit (onset date, swab date, other)	Comments
Example1	01/10/2020	31/12/2020	1	Date of onset	(this is only an example; all specimens were characterised)
Example2	01/01/2021	15/02/2021	0.2	Date of onset	(this is only an example; 20% of all specimens were characterised)

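### Variant- and clade-specific VE rests on successfully sequenced cases only; random selection does not cover later sequencing failure, and no analysis checks whether failure differs by vaccination status

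*Protocol*

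**What the plan says.** Section 2.2 sets a secondary objective "to estimate IVE and CVE against specific influenza (sub)clades or SARS-CoV-2 genetic variants". Section 3.4 has matching outcomes: for influenza, "laboratory-confirmed influenza by clade/genetic variant (where possible"), and for COVID-19, "Secondary outcomes of interest, in the same patient group at primary care level, will be genetic variants of SARS-CoV-2".

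Section 3.6 says how the genetic information arises: "a systematic sample of isolates (or all isolates) will undergo gene sequencing". On the sample it says "The sample should be random and thus be representative of cases", and that it should be large enough for "reasonable precision when calculating proportions of virus change over time". Sites are to state their sampling fraction over time, "as well as describing numbers of viruses not sequenced due to CT values or other technical reasons".

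Annex 2 gives a data form (Table A2) with columns for selection, reason for not characterising and CT value. Its text treats these as optional additions to the ID and accession number. Table A3 documents sampling fractions, with an illustrative row in which "20% of all specimens were characterised".

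Annex 4 puts study site and onset time in every pooled model. Neither Annex 4 nor the sensitivity list in 3.13.2 compares sequenced with unsequenced cases, and the bias discussion in sections 5.1 and 5.2 does not mention the issue.

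**The concern.** A PCR-positive patient without a usable sequence has no clade or variant. That patient cannot be a case for a given variant and is not a test-negative control, so drops out of the variant-specific analysis, while all controls stay in.

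Two filters act on cases: selection for sequencing, then success of sequencing. Random selection makes the first harmless to the odds ratio. The second comes later and, where CT value is the reason, depends on the specimen. The protocol does not separate the two, and it asks for neither filter by vaccination status.

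At stake is the comparison this objective serves: whether VE against one variant differs from VE against another, or from overall VE. If vaccinated cases fail sequencing more or less often than unvaccinated cases, part of an apparent difference between variant-specific and overall VE could come from the laboratory step. Section 5.2 already accepts the principle for participation: lack of representativeness matters most when it is differential by case and vaccination status. The protocol does not apply this to sequencing.

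**Working it through.** **Inputs.** From the protocol: VE = (1 − OR) × 100 from logistic regression (3.13.1, Annex 4); the Table 4 row with precision 0.2, OR 0.5, coverage 0.5 and 289 cases and 289 controls (3.10); the example sequencing fraction 0.2 (Table A3). Assumed, because the protocol gives none: sequencing success s_v in vaccinated and s_u in unvaccinated cases.

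**Step 1: reproduce the plan's figure.** With p0 = 0.5 and p1 = 0.5 × 0.5/(0.5 + 0.5 × 0.5) = 1/3, the precision formula is n = [1/(p0(1 − p0)) + 1/(p1(1 − p1))] × (1.96/ln((OR + d)/OR))². This gives (4 + 4.5) × (1.96/ln 1.4)² = 288.4, rounded up to 289, with VE 50% and interval 30.0 to 64.3. All 73 rows of Table 4 reproduce within one patient, so the table is not in question. It contains no variant-specific sample size.

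**Step 2: effect of sequencing on the odds ratio.** Within a site and period, let A and B be the vaccinated and unvaccinated cases of one variant, and C and D the vaccinated and unvaccinated controls. The true OR is AD/(BC). Only s_v·A and s_u·B are observed, so

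OR_obs = (s_v·A·D)/(s_u·B·C) = r × OR_true, with r = s_v/s_u.

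Strictly, r is the ratio among cases of the variant analysed.

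**Step 3: size for assumed r.**

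| r (assumed) | True VE 30% becomes | True VE 50% becomes |
|---|---|---|
| 1 | 30% | 50% |
| 0.95 | 33.5% | 52.5% |
| 0.9 | 37% | 55% |
| 0.8 | 44% | 60% |
| 0.8/0.7 = 1.14 | 20.0% | 42.9% |

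For example, 1 − 0.9 × 0.5 = 0.55.

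**Step 4: loss that does not bias.** In the 289/289 row, treating all cases as one variant, random selection of 20% leaves about 58 typed cases: VE stays 50% and the interval widens to 9.5 to 72.4. Success of 80% in both groups leaves 231 typed cases: VE stays 50%, interval 28.5 to 65.0.

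**Step 5: loss that does.** In the same row, s_u = 0.8 and s_v = 0.7 leave 192.7 × 0.8 + 96.3 × 0.7 = about 222 typed cases. OR_obs = 0.5 × 0.875 = 0.4375, so VE is 56.25%, interval 36.8 to 69.7. A larger sample narrows this interval around the wrong value.

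**Step 6: can weighting do harm?** Suppose success depends on variant only: 0.9 for variant 1 and 0.6 for variant 2. Let the variant mix be 30/70 in vaccinated and 50/50 in unvaccinated cases. Within each variant r = 1, so the unweighted estimate is unbiased. Success over all variants is 0.3 × 0.9 + 0.7 × 0.6 = 0.69 in vaccinated and 0.5 × 0.9 + 0.5 × 0.6 = 0.75 in unvaccinated cases. Weights built on vaccination status alone multiply the OR by 0.75/0.69 = 1.087 and move a correct 50% to about 46%. Weighting therefore belongs in a sensitivity analysis.

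**The case against.** The strongest reply is that section 3.6 contains no false statement. The quoted sentence is a requirement on how isolates are chosen, with a size set for describing virus change, and it is right for that purpose. A reader might infer that the protocol calls the successfully sequenced cases representative; it never says so. It foresees failures, asks sites to count them, and provides form fields for the reasons. This stands. What is missing is the distinction between selected and sequenced cases, and any use of the recorded failures in the analysis.

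A reader might also infer from the Table A3 row that losing 80% of cases biases variant-specific VE. It does not: the row is marked as an example, the fraction is a random one, and r = 1.

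Nor do sampling fractions that change over time or between sites form a serious gap. Site and onset time are in every pooled model and largely absorb them. What remains is failure linked to vaccination within a site and period.

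Finally, the documents give no failure rate and no evidence that failure differs by vaccination status. To say that variant-specific VE is biased, or inflated, would go beyond them. The limits on onset-to-swab delay in 3.7.3 (seven days for IVE, ten for CVE) may also narrow CT-related loss.

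One could leave the matter to a later analysis plan. But this protocol carries its own detailed pooled analysis plan, sensitivity list and bias section, and the gap lies across all three.

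**Conclusion.** The point holds as a conditional one. Variant- and clade-specific VE is exposed to a bias that random selection, larger samples and the planned site and time terms do not remove. Its factor on the odds ratio is r, and it is zero when r = 1. Size and sign are unknown: over the assumed range from 0.8 to 1.14, a true VE of 50% would be read as anything from 60% to 43%. The result assumes that controls are unaffected by sequencing and that r applies within site, period and variant. The primary objective, overall and product-specific VE, is untouched because it needs no sequence. The change is worth making because much of the needed information is already in the dataset and the check bears directly on how a difference between variants can be read.

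**What to change.** 1. In section 3.6, limit the representativeness statement to selection, and say that it does not extend to the successfully sequenced subset.
2. Beside each variant- or clade-specific estimate, report the proportion of PCR-positive cases selected, and the proportion successfully sequenced, by vaccination status, site and period.
3. Add a sensitivity analysis to 3.13.2 and Annex 4. Either weight sequenced cases by the inverse of their estimated probability of a usable sequence, or show VE over a stated range of r. The weighting model would use site, onset period with the Table A3 fraction, vaccination status, age, onset-to-swab delay and, where collected, CT value, with robust standard errors. Keep the unweighted model as the main analysis.
4. List this bias in section 5.1.

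The cost is one table, one extra model and wider intervals. Onset date, swab date, age and vaccination are non-optional items in Table A1. Sequence identifiers and variant or clade are optional there, and CT value, selection and failure reason are optional in Annex 2, so weighting on CT depends on sites collecting it. The weights are valid only if variant is unrelated to sequencing success given the modelled variables. The tabulated ratio covers all variants together, so it is a guide to r and not r itself. While editing 3.6, correct its pointer to a Table 9 in Annex 2, where the tables are numbered A2 and A3.

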3.7 Study participant identification

3.7.1 Selection of patients to swab

Study participants are patients with symptoms compatible with suspected COVID-19, as described in section 3.5, consulting a participating GP. Consultation is defined as:

- Having a face-to-face consultation with the GP (in the practice or at the patient's home);
- Having a telephone/video consultation with the GP⁴ and then having a swab collected soon after the consultation, either by:
 - A referral to a dedicated COVID-19/respiratory testing centre;
 - A referral to a medical laboratory/specimen collection centre;
 - Having a swab collected by a physician or nurse:
 - At the GP's practice;
 - At a patient's home.

Following the procedures outlined by each study, all or a systematic sample of patients are selected and asked to provide a swab specimen for laboratory testing. Sampling all suspected influenza or COVID-19 cases is preferred, in particular all patients aged 65 years and over for influenza. If this is not possible, then a systematic sample with known sampling fraction can be taken, e.g. the first three suspected cases seen each week per GP, including all patients aged 65 years and over.

- *Each study site to describe the procedures to select suspected influenza and COVID-19 cases to swab.*
- *Each study to describe how/where/by whom swabs will be collected.*

3.7.2 Patient inclusion criteria

Patients are eligible if they meet the inclusion definition and consent to participate (the patient or her/his legal guardian gave consent to participate according to the local ethical review process).

- *Each study site to describe country procedures for oral informed consent or written informed consent and specify these in the study annexes.*

3.7.3 Patient exclusion criteria

Patients are **excluded from the primary analysis** if they:

- refuse to participate in the study;
- are not swabbed;
- are unable to give informed consent or follow an interview in their native language because of aphasia, reduced consciousness, or other reasons;
- cannot be swabbed due to severe septum deviation, obstruction or other conditions that contra-indicate swabbing;
- have contraindications for the influenza (for IVE) or COVID-19 vaccination (for CVE);
- are institutionalised (virus exposure and risk factors may be different – specific cohort studies can be undertaken in these groups);
- are swabbed more than seven days (IVE) or 10 days (CVE) after symptom onset (to avoid false negatives; other numbers of days can be explored in sensitivity analyses);
- were vaccinated with a two-dose vaccine with fewer days between dose 1 and 2 than recommended by the manufacturer;
- had an inconclusive RT-PCR test.
- for IVE:
 - patients who had tested positive before to any influenza virus in the current season;
 - patients who had received antivirals 2 weeks prior to swabbing;

⁴ In certain circumstances, e.g. if COVID-19 testing centres are physician led, a consultation with a GP is not needed prior to the swab.

- for CVE:
 - patients who had tested previously positive to SARS-CoV-2 within 60 days prior to the current illness episode (other numbers of days and scenarios where date of previous test is unknown will be explored in sensitivity analyses);
 - controls positive to a seasonal coronavirus (e.g. HCoV-NL63, HCoV-229E, HCoV-OC43 and HCoV-HKU1) (as they may be affected by the vaccination).

Reasons for exclusion are documented.

Study sites can collect information on the exclusion factors and exclude patients according to available evidence on these factors.

In the main analysis, patients will be excluded if they were vaccinated with their most recent vaccine dose within 1–13 days preceding symptom onset (see section 3.8). In secondary analyses by time since vaccination, these patients could be included.

In sensitivity analyses, study sites can carry out the VE analyses with different cut-offs of numbers of days between onset and swabbing, using (for example) 5 and 7 days (see section 3.13.2).

In further sensitivity analyses, patients reporting testing previously positive to SARS-CoV-2 will be included, and if sample size allows, an analysis stratified by previous infection will be carried out. Additionally, if sample size allows, patients testing previously positive to SARS-CoV-2 will be included or excluded with varying days since last infection, or variant of infection, if this information is available.

Please see section 3.13.2 on sensitivity analyses.

3.7.4 Restriction to priority groups for vaccination for IVE and CVE

IVE will be estimated in the influenza vaccine target group, although as many people have the opportunity to receive influenza vaccine outside the designated target groups, IVE in the general population will also be estimated.

For CVE, patients will be included in the analysis if they are part of a target group for COVID-19 vaccination (particularly booster vaccination), at time of swab. Different vaccine target groups can be used, such as target group for primary course vaccination, or target group for booster vaccination. For some of these target groups, e.g. target group for booster vaccination, country-specific recommendations of time between last dose and current dose need to be taken into account (e.g. 3 or 5 months since last vaccination). As many people have had (and will continue to have) the opportunity to receive COVID-19 vaccine outside the designated target groups, CVE in the general population will also be estimated.

3.8 Exposure (vaccination)

3.8.1 Definition of vaccination status

Current seasonal influenza vaccine

An individual is considered as:

- vaccinated against influenza if they received one dose of the (product-specific) current season influenza vaccine 14 or more days before disease onset;
- unvaccinated if they
- unvaccinated if they:
 - did not receive influenza vaccine in the current season; or
 - received one dose of the (product-specific) current season influenza vaccine less than 14 days before disease onset; or
 - were vaccinated after their symptom onset date.

Current pandemic COVID-19 vaccine

COVID-19 vaccination rollout schedules are evolving and this section will need to be updated on an ongoing basis to reflect any new vaccination schedules.

An individual will be considered as vaccinated against COVID-19 with a product-specific vaccine under the following categories:

- **Fully vaccinated with a primary course, first booster plus second booster:** Patients will be considered fully vaccinated with second booster if they have **received completed primary course vaccination plus booster (see below) followed by a second booster dose** at least 14 days* before symptom onset.
- **Fully vaccinated with a primary course plus booster:** Patients will be considered fully vaccinated with booster if they have **received completed primary course vaccination (see below) followed by a booster dose** at least 14 days* before symptom onset.

- **Fully vaccinated with a primary course** (two-dose vaccine): Patients will be considered fully vaccinated if they have **received both doses** at least 14 days⁵ before symptom onset.
- **Fully vaccinated with a primary course** (single-dose vaccine): Patients will be considered fully vaccinated if they have **received one dose** at least 14 days⁵ before symptom onset.
- **Partially vaccinated** (two-dose vaccine only): Patients will be considered partially vaccinated if they have **received one of two doses** at least 14 days⁵ before symptom onset.
- Patients will be considered as **unvaccinated** if they **did not receive COVID-19 vaccine** or if they **were vaccinated after onset** of symptoms.

As the COVID-19 vaccine schedules evolve, collecting detailed vaccination information including dates of each individual vaccination may become complicated and burdensome, particularly when the data source for vaccine information is not electronic. As a minimum, study sites should collect information on number of doses of COVID-19 vaccine and date and brand of last vaccine received. It is highly recommended to collect the brands of each COVID-19 vaccine received if possible, most importantly the brand of the first dose (to differentiate between primary course with single-dose vs two-dose vaccines) and the brand of the last dose.

- *Each study site to describe the country COVID-19 vaccination recommendations and schedule, including specific recommendations by age/at-risk groups, and policy regarding timings between doses of primary course and booster doses, as well as the timing of vaccine rollout.*
- *Each study site to describe the vaccination variables they are collecting.*

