3.3 Study period

The study period for seasonal IVE starts when the seasonal influenza vaccine of the corresponding season becomes available and the influenza season begins in the country/region, and will finish at the end of the influenza period². Cases and controls are included from the week of onset of the first influenza positive case presenting in each country-specific study.

The study period for CVE starts when the COVID-19 vaccine is available for the target group of interest in each of the participating countries and when SARS-CoV-2 is circulating. The study period is defined for each priority vaccination group, and begins for each vaccination group, when vaccination campaign in this group begins.

Physicians in participating primary care practices recruit patients and collect data throughout the year.

- *Study sites to define the beginning of the study period for the IVE/CVE study (date/month/year).*
- *Each study site specifies the date of the start of their influenza/COVID-19 vaccination campaign for each priority vaccination group, for the vaccine products used, including recommendations for delay between first, second and subsequent doses (if applicable).*

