3.13.2 Sensitivity analyses

As sensitivity analyses, study sites can measure VE:

- with different cut-offs of numbers of days between onset and swabbing;
- with different cut-offs of numbers of days between vaccination and onset of symptoms;
- varying the time period post-vaccination (e.g. seven days, 14 days, 15-30 days, 30-59 days, etc.) to be considered 'fully vaccinated' or 'partially vaccinated' (see section 3.8.1);
- including, excluding and stratifying by those with previous positive tests, and also with different delays between previous test and inclusion in the study;

- excluding patients testing positive at home as part of the current illness episode and testing negative as part of the study;
- using only controls positive to other respiratory viruses;
- excluding controls testing SARS-CoV-2 positive (IVE) or influenza positive (CVE), or adjusting by COVID-19 (IVE) or influenza (CVE) vaccination (see also section 5.1.7);
- including those fully vaccinated but with inappropriate gaps between doses.

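### Sections 3.7.3 and 3.8.1 treat influenza vaccinees with onset within 14 days of the dose differently, so the reference group of the primary IVE analysis is contradictory; any bias depends on the effect in days 0–13

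*Protocol*

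**What the plan says.** Section 3.7.3, after its separate lists of IVE-only and CVE-only exclusions, states: "In the main analysis, patients will be excluded if they were vaccinated with their most recent vaccine dose within 1–13 days preceding symptom onset". It points to section 3.8 and adds: "In secondary analyses by time since vaccination, these patients could be included". Nothing restricts the sentence to COVID-19 vaccine.

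Section 3.8.1 (influenza) defines as exposed those "vaccinated against influenza if they received one dose of the (product-specific) current season influenza vaccine 14 or more days before disease onset". Its unvaccinated group includes anyone who "received one dose of the (product-specific) current season influenza vaccine less than 14 days before disease onset". It mentions no exclusion.

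The COVID-19 part of 3.8.1 has no such clause: "Patients will be considered as unvaccinated if they did not receive COVID-19 vaccine or if they were vaccinated after onset of symptoms".

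Section 3.13.2 lets sites vary the rule as a sensitivity analysis, "with different cut-offs of numbers of days between vaccination and onset of symptoms", but does not settle the primary one.

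**The concern.** The same influenza patients leave the main analysis under one section and join its reference group under the other. The COVID-19 definition agrees with 3.7.3, so the influenza clause is the outlier.

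Who forms the reference group determines what the odds ratio compares. The primary objective (section 2.1) covers each site's estimate as well as the pooled one, so two sites that both follow the protocol could report different contrasts. Annex 4 puts country-specific estimates into forest plots, the Q-test, I² and a two-stage meta-analysis. A difference of definition would look like heterogeneity there.

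The issue grows when recruitment overlaps the vaccination campaign. Section 3.3 allows some overlap: "The study period for seasonal IVE starts when the seasonal influenza vaccine of the corresponding season becomes available" and the influenza season begins. Section 1.2 calls early-season IVE critical for vaccine composition discussions.

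Day 0 is also handled unevenly. A dose on the onset day falls outside 1–13 days in 3.7.3, yet counts as unvaccinated for influenza in 3.8.1. For COVID-19, a first-ever dose on that day is neither at least 14 days before onset nor after onset.

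**Working it through.** **1. The plan's nearest figure.** The protocol gives no figure for recent vaccinees. The closest anchor is the Table 4 row for OR 0.5, coverage 30% and lower-bound precision 0.2: 395 cases, 395 controls, VE 50% (30–64).

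- p0 = 0.30; p1 = 0.5×0.30/(0.70 + 0.5×0.30) = 0.1765.
- n = [1/(p0(1−p0)) + 1/(p1(1−p1))] / [ln((OR+d)/OR)/1.96]² = (4.762 + 6.881)/(0.3365/1.96)² = 395.1. The row reproduces.
- Upper VE limit: 1 − 0.5²/0.7 = 64.3%.

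**2. Bias formula.** Let v be true IVE for doses at least 14 days before onset, e the effect of a dose in days 0–13, and s the share of recent vaccinees among controls classed as unvaccinated under 3.8.1. Relative to truly unvaccinated people, that mixed group has case odds (1−s) + s(1−e) = 1 − s·e. So:

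- following 3.8.1: IVE = 1 − (1−v)/(1 − s·e);
- following 3.7.3 (exclusion): IVE = v, whatever e is.

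**3. Two scenarios (assumed v = 50%, e = 30%).**

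- 5% of the source population recently vaccinated, 40% vaccinated at least 14 days ago, 55% unvaccinated: s = 5/60 = 8.3%; 1 − s·e = 58.5/60 = 0.975; IVE = 1 − 0.5/0.975 = 48.7%.
- 15% recent, 35% at least 14 days ago, 50% unvaccinated: s = 15/65 = 23.1%; 1 − s·e = 60.5/65 = 0.931; IVE = 1 − 0.5/0.931 = 46.3%.

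**4. Range, because the protocol states neither s nor e.** IVE under 3.8.1 with v = 50%:

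| e | s = 5% | s = 10% | s = 20% | s = 30% |
|---|---|---|---|---|
| −25% (higher odds) | 50.6 | 51.2 | 52.4 | 53.5 |
| 0 | 50.0 | 50.0 | 50.0 | 50.0 |
| 25% | 49.4 | 48.7 | 47.4 | 45.9 |
| 50% | 48.7 | 47.4 | 44.4 | 41.2 |

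**5. On the scale of the Table 4 row.** Take 395 cases and 395 controls, coverage 30%, and 10% of controls recently vaccinated, so s = 10/70 = 14.3%. Section 3.8.1 gives:

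- e = −25%: 51.7% (32.3–65.6);
- e = 0: 50.0% (30.0–64.3);
- e = 25%: 48.1% (27.6–62.9);
- e = 50%: 46.2% (25.0–61.4).

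Exclusion gives 50.0% in all four cases, with lower limits of 29.3% to 30.0% and upper limits of 64.3% to 64.6%. It therefore costs almost no precision here.

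**The case against.** **The sections can be read in sequence.** Section 3.7.3 governs the main analysis and 3.8.1 is a general status definition. If the exclusion comes first, nobody with a dose 1–13 days before onset reaches the reference group. This is a fair reading, but neither section states it. Under it, the 3.8.1 clause does nothing in the main analysis except on day 0. In the secondary analyses where these patients may return, it would still label them unvaccinated.

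**A reader might infer that IVE is necessarily biased downwards.** The protocol does not support this: it gives no effect for days 0–13. The table above shows no bias if that effect is nil and upward bias if recent vaccinees have higher odds.

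**A reader might infer that the primary pooled model will mix two exposure definitions.** That is largely answered. The primary pooled analysis is one-stage on individual data (Annex 4), cleaned by a central hub (section 3.13.3). Annex 1 lists onset date and influenza vaccination date among variables not headed optional. The hub can apply one rule wherever dates are supplied. What remains exposed are the site-level estimates, the heterogeneity statistics and two-stage analysis that use study-specific estimates, and sites without precise vaccination dates, which section 3.8.2 allows for.

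**The shifts are small and the overlap is limited.** The two scenarios move IVE by 1.3 and 3.7 points, against the 10–30 points of lower-bound precision planned in section 3.10. Section 3.3 starts inclusion only in the week of onset of the first influenza-positive case, which restricts overlap with the campaign. Both points stand and bear on severity.

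**A reader might infer that a COVID-19 dose on the onset day never has a class.** That goes too far. A patient with a complete primary course at least 14 days earlier and a booster on the onset day still meets the primary-course definition. The gap concerns mainly a first-ever dose on that day.

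**Conclusion.** The contradiction is in the text and concerns the primary IVE exposure, so it should be fixed. It does not depend on the direction of any bias.

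Following 3.8.1 recovers the true IVE only if vaccination has no effect in days 0–13; following 3.7.3 recovers it in every case examined. At an assumed true IVE of 50%, 30% early protection and recent vaccinees at 8% to 23% of the nominal reference group, the reading is 48.7% to 46.3%. Over the wider grid it runs from 41.2% to 53.5%. All of these rest on assumed shares and early effects, and on recent vaccination being the only departure from an otherwise unbiased comparison.

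The consequence is greatest for early-season estimates and for the analyses built on site-level results. The modest shifts, and the hub's ability to recode dated records, make this a correction of wording and not a threat to the design.

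**What to change.** - **One primary rule in both sections.** State that influenza vaccinees with a dose 0–13 days before onset are excluded from the main IVE analysis.
- **Section 3.8.1, influenza.** Replace the bullet that classes a dose less than 14 days before onset as unvaccinated with a separate category, recently vaccinated (0–13 days), for the time-since-vaccination analyses. Deleting the bullet alone would leave these patients without a status where 3.7.3 lets them return.
- **Section 3.13.2.** Keep counting them as unvaccinated only as a named sensitivity analysis.
- **Section 3.7.3.** Change 1–13 to 0–13 days, so that a dose on the onset day is assigned for both IVE and CVE.

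The cost is protocol wording, and a few recently vaccinated patients leave the main IVE analysis. No new data are needed where vaccination dates are collected. Sites without dates should say in their annex that they cannot apply the rule.
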